#### Pharmacokinetics

The pharmacokinetic parameters listed in Section [2.1](#) and [2.2](#) for BI 1358894 and BI 1361608 will be calculated according to the relevant Standard Operating Procedure (SOP) of the Sponsor ([001-MCS-36-472](#)). Pharmacokinetic analyses will be performed using validated software programs, normally Phoenix Winnonlin (Pharsight®) with applications validated for the respective purpose. Graphs and tables will be generated using validated customised SAS®

Proprietary confidential information © 2019 Boehringer Ingelheim International GmbH or one or more of its affiliated companies

macros or appropriate graphic software. A reference to the software used, e.g., name, will be indicated in the CTR.

Plasma and urine concentration data and parameters of a subject will be included in the statistical pharmacokinetic (PK) analyses if they are not flagged for exclusion due to a protocol deviation relevant to the evaluation of PK (to be decided no later than in the Report Planning Meeting) or due to PK non-evaluability (as revealed during data analysis, based on the criteria specified below). Exclusion of a subject's data will be documented in the CTR.

Relevant protocol deviations may be:

- Incorrect trial medication taken, i.e., the subject received at least one dose of trial medication the subject was not assigned to
- Incorrect dose of trial medication taken
- Use of restricted medications

Plasma and urine concentrations and/or parameters of a subject will be considered as non-evaluable, if for example

- The subject experienced emesis that occurred at or before two times median  $t_{max}$  of the respective treatment (Median  $t_{max}$  is to be determined excluding the subjects experiencing emesis),
- Missing samples/concentration data at important phases of PK disposition curve.

Plasma/urine concentration data and parameters of a subject which is flagged for exclusion will be reported with its individual values but will not be included in the statistical analyses.

Only concentration values within the validated concentration range and actual sampling times will be used for the calculation of pharmacokinetic parameters. Concentrations used in the pharmacokinetic calculations will be in the same format as in the bioanalytical report (that is to the same number of decimal places provided in the bioanalytical report).

### **7.3.1 Primary endpoint analyses**

The primary endpoint as specified in Section [2.1.2](#) will be derived according to BI standards. The analysis will be based on the treated set (TS) and will be descriptive in nature.

### **7.3.2 Secondary endpoint analyses**

The secondary endpoints (refer to Section [2.1.3](#)) will be analysed descriptively.

#### Further exploratory analyses

Dose proportionality will be explored via graphical checks and if applicable via the power model stated below. The analysis will be performed for the pharmacokinetic endpoints ( $AUC_{0-tz}$ ,  $AUC_{0-\infty}$  and  $C_{max}$ ) specified in Section 2.1.3.

The power model describes the functional relationship between the dose level and PK endpoint on the log scale via

$$y_{km} = \log(x_{km}) = \mu + \beta \cdot \log(D_k) + e_{km},$$

where

$y_{km}$  logarithm of response (PK parameter) measured on subject m receiving dose k,  
 $\mu$  the overall mean,  
 $\beta$  slope parameter of linear regression line,  
 $D_k$  level of dose k,  $k=1,\dots,3$ ,  
 $e_{km}$  the random error associated with the mth subject who was administered dose k  
( $e_{km} \sim N(0, \sigma^2)$  iid).

The slope parameter  $\beta$  together with its two-sided 90% confidence interval will be estimated.

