## CLINICAL TRIAL PROTOCOL SYNOPSIS

Company name	Boehringer Ingelheim
Protocol date	17 Jan 2019
Revision date	Not applicable
BI trial number	1402-0008
Title of trial	Safety, tolerability and pharmacokinetics of single rising oral doses of BI 1358894 in healthy Japanese male subjects (double-blind, randomised, placebo-controlled parallel dose group design)
Principal Investigator	
Trial site	
Clinical phase	I
Trial rationale	The objective of this trial is to investigate the safety, tolerability, and pharmacokinetics of BI 1358894 in healthy Japanese male subjects. The chosen population of healthy male volunteers using single rising oral doses is considered adequate to provide the basis for the clinical development program of BI 1358894 in Japan.
Trial objectives	To investigate safety, tolerability and pharmacokinetics following single rising doses of BI 1358894
Trial endpoints	Primary endpoint The number [N(%)] of subjects with drug related adverse events Secondary endpoints: AUC 0-tz , C max , AUC 0-∞ (if evaluable) of BI 1358894
Trial design	Double-blind, randomised, placebo-controlled within parallel dose groups
Number of subjects	
total entered	24
each treatment	8 per dose group (6 on BI 1358894 and 2 on placebo)
Diagnosis	Not applicable
Main criteria for inclusion	Healthy Japanese male subjects, age of 20 to 45 years (inclusive), body mass index (BMI) of 18.5 to 25.0 kg/m  (inclusive)
Test product(s)	BI 1358894 film-coated tablet (25 mg, 100 mg)

Proprietary confidential information © 2019 Boehringer Ingelheim International GmbH or one or more of its affiliated companies

dose	50 mg, 100 mg, and 200 mg
mode of admin.	Oral with 240 mL of water after a high-calorie, high-fat breakfast
Comparator product(s)	Matching placebo(s)
dose	Not applicable
mode of admin.	Oral with 240 mL of water after a high-calorie, high-fat breakfast
Duration of treatment	Single dose
Statistical methods	Descriptive statistics will be calculated for all endpoints.

Proprietary confidential information © 2019 Boehringer Ingelheim International GmbH or one or more of its affiliated companies

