#### **2.1.3 Secondary endpoint**

The following pharmacokinetic parameters will be determined for BI 1358894 if feasible:

- $AUC_{0-tz}$  (area under the concentration-time curve of the analyte in plasma over the time interval from 0 to the last quantifiable data time point  $t_z$ )
- $AUC_{0-\infty}$  (area under the concentration-time curve of the analyte in plasma over the time interval from 0 extrapolated to infinity)
- $C_{max}$  (maximum measured concentration of the analyte in plasma)

Proprietary confidential information © 2019 Boehringer Ingelheim International GmbH or one or more of its affiliated companies

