### 7.2 NULL AND ALTERNATIVE HYPOTHESES

It is not planned to test any statistical hypotheses in this study.

Any confidence intervals (CIs) computed are to be interpreted in the perspective of the exploratory character of the study; i.e., CIs are considered as interval estimates for effects.

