2. LIST OF ABBREVIATIONS

See Medicine Glossary:

website: glossary

Term	Definition / description
ALT	Alanine Aminotransferase
ANCOVA	Analysis of covariance
AST	Aspartate Aminotransferase
AUC _{0-tz}	Area under the concentration-time curve of the analyte in plasma over the time interval from 0 to the last quantifiable data point
AUC _{0-∞}	Area under the concentration-time curve of the analyte in plasma over the time interval from 0 extrapolated to infinity
BMI	Body mass index
BP	Blood pressure
CARE	Clinical Analysis and Reporting Environment
CI	Confidence Interval
C _{max}	Maximum measured concentration of the analyte in plasma
CV	Arithmetic Coefficient of Variation
DB	Dose Proportionality, Between-Subject Design
DILI	Drug induced liver injury
ECGPCS	ECG Pharmacokinetic Concentration Set
gCV	Geometric Coefficient of Variation
gMean	Geometric Mean
HR	Heart rate
IQRMP	Integrated Quality and Risk Management Plan
LLT	Lower Level Term
Max	Maximum
MedDRA	Medical Dictionary For Regulatory Activities
Min	Minimum
N	Number non-missing observations
P10	10 th percentile
P90	90 th percentile
PKS	Pharmacokinetic parameter analysis set

Term	Definition / description
PR	Pulse rate
Q1	1 st quartile
Q3	3 rd quartile
QD	Quaque die, once daily
RAGe	Report Appendix Generator system
REP	Residual Effect Period
RR	Respiratory rate
SAS [®]	Statistical Analysis System
SD	Standard Deviation
SOC	System Organ Class
TS	Treated Set
ULN	Upper Limit of Normal
WHO-DD	World Health Organization Drug Dictionary

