4. CHANGES IN THE PLANNED ANALYSIS OF THE STUDY

All analyses described in the TSAP are outlined in the CTP. The following changes compared to the protocol will be made:

In the protocol, it is stated that the medical examination at screening will include alcohol history. However, alcohol history is not captured in the eCRF, and thus, will neither be listed nor included in tables.

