7.5.2 Secondary endpoints

7.7 EXTENT OF EXPOSURE

Descriptive statistics are planned for this section of the report based on the TS. The date and time of drug administration will be listed for each subject.

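### If 200 mg is still quantifiable after 192 h, the planned AUC0-tz power-model slope is biased upward, because plasma sampling stops at 192 h for 50 and 100 mg but runs to 672 h for 200 mg

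*Protocol*

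**What the plan says.** Protocol section 7.3.2 (Further exploratory analyses) states: "Dose proportionality will be explored via graphical checks and if applicable via the power model stated below". It continues: "The analysis will be performed for the pharmacokinetic endpoints", and names AUC0-tz, AUC0-∞ and Cmax. One log-log regression is fitted across 50, 100 and 200 mg, and the slope is reported with a two-sided 90% confidence interval.

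Protocol section 2.1.3 defines AUC0-tz as the area "over the time interval from 0 to the last quantifiable data time point". The synopsis lists AUC0-∞ only if it can be evaluated.

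The Flow Chart for Dose Groups 1 and 2 has its last plasma sample at 192 h. The columns of that table are displaced in the copy reviewed. The reading rests on the row pattern, which matches the Dose Group 3 chart. Dose Group 3 is also sampled at 192 h, and then at 240, 336, 504 and 672 h.

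Protocol section 7.2 plans no hypothesis test: "CIs are considered as interval estimates for effects". SAP section 4 says "All analyses described in the TSAP are outlined in the CTP", and the one change it lists concerns alcohol history, not the power model.

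**The concern.** AUC0-tz has one name but can cover different windows. By schedule, tz cannot pass 192 h at 50 and 100 mg but can reach 672 h at 200 mg. The window is therefore tied to dose, the regressor. If 200 mg subjects are quantifiable after 192 h, their AUC0-tz holds a larger share of total exposure than it does at 50 mg, and the slope exceeds 1 even when exposure is exactly proportional.

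At stake is the meaning of an estimate, not an error rate. The slope would mix dose proportionality with the sampling schedule, and at long half-lives it could make less-than-proportional exposure look proportional. Protocol section 1.3 says the PK data will help define doses for later studies.

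**Working it through.** **Inputs from the documents.** Doses 50, 100 and 200 mg; 6 active subjects per dose (protocol section 3.1); last plasma sample at 192, 192 and 672 h (Flow Charts). The plan gives no expected slope, and its sample size is not power-based, so there is no figure to reproduce.

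**Assumed inputs.** One compartment, ka = 0.5/h, and half-life, LLOQ and CV varied over ranges.

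**1. Slope.** The centred log doses are −ln 2, 0 and +ln 2. With 6 per dose, Sxx = 6 × 2 × (ln 2)² = 5.765, and the slope is ln(gMean at 200 mg / gMean at 50 mg) / (2 ln 2). The 100 mg group has no weight.

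**2. Share of AUC0-∞ captured by time T.** F(T) = 1 − [ka·exp(−kT) − k·exp(−ka·T)] / (ka − k), with k = ln 2 / half-life. For a proportional drug quantifiable to its last sample, slope = 1 + ln[F(672)/F(192)] / (2 ln 2). At 100 h: F(192) = 0.732, F(672) = 0.990, ratio 1.353, slope = 1 + 0.302/1.386 = 1.218.

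| Half-life (h) | F(192) | F(672) | Slope (true 1) |
|---|---|---|---|
| 24 | 0.996 | 1.000 | 1.003 |
| 36 | 0.974 | 1.000 | 1.019 |
| 50 | 0.928 | 1.000 | 1.054 |
| 75 | 0.827 | 0.998 | 1.135 |
| 100 | 0.732 | 0.990 | 1.218 |
| 150 | 0.584 | 0.955 | 1.354 |

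**3. Schedule or LLOQ?** Each cell gives the slope on the planned schedules / the slope with every group cut at 192 h. LLOQ is a percentage of the 200 mg peak.

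| Half-life (h) | LLOQ 1% | LLOQ 2% | LLOQ 5% |
|---|---|---|---|
| 36 | 1.02 / 1.01 | 1.06 / 1.06 | 1.17 / 1.17 |
| 50 | 1.05 / 1.00 | 1.05 / 1.02 | 1.10 / 1.10 |
| 75 | 1.13 / 1.00 | 1.10 / 1.00 | 1.09 / 1.04 |
| 100 | 1.22 / 1.00 | 1.20 / 1.00 | 1.15 / 1.00 |

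Where the second figure is 1.00, the unequal schedule explains the whole bias. Where the two figures agree, it is ordinary LLOQ truncation.

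**4. Against precision.** The 90% CI half-width is t(0.95, 16 df) × √ln(1 + CV²) / √5.765. At CV 30% this is 1.746 × 0.294 / 2.401 = 0.21. At CV 20, 30, 40 and 50% it is 0.14, 0.21, 0.28 and 0.34. With full quantifiability, the bias exceeds it only from half-lives of about 78, 99, 121 and 145 h.

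**5. True non-proportionality.** Let clearance change only at 200 mg, by a factor f, with volume fixed. The true slope is 1 + ln(1/f)/(2 ln 2), and the half-life at 200 mg is the baseline half-life divided by f. All samples are taken as quantifiable.

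| Baseline half-life (h) | f = 1.35, true 0.78: AUC0-tz | f = 2/3, true 1.29: AUC0-tz | f = 2/3, true 1.29: AUC0-192 |
|---|---|---|---|
| 24 | 0.79 | – | – |
| 36 | 0.80 | 1.31 | 1.25 |
| 50 | 0.84 | 1.34 | 1.21 |
| 75 | 0.92 | 1.42 | 1.16 |
| 100 | 1.01 | 1.48 | 1.13 |

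**6. AUC0-∞.** At 100 h the extrapolated share is 1 − 0.732 = 27% at 50 and 100 mg, against 1 − 0.990 = 1% at 200 mg.

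**7. Common window.** For a proportional drug, AUC0-192 gives a slope of 1.00 at every half-life tried. A simulation with noise agrees (2,500 trials per cell; clearance and volume CV about 21% each; assay CV 10%; half-lives 50, 75 and 100 h; LLOQ 1% and 5%). Mean slopes were 1.05 to 1.22 for AUC0-tz, 0.97 to 1.00 for AUC0-∞ and 1.00 for AUC0-192.

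**The case against.** The strongest reply is that the plan already carries its own check. The same model is fitted to AUC0-∞ and Cmax. Cmax is unaffected, and in the simulation the AUC0-∞ slope stayed near 1. A reader who sees 1.22 beside 0.98 will suspect truncation. This stands in part, and it is why the point is not major. It is weakest where the bias is largest: AUC0-∞ is conditional on being evaluable, and at a long half-life it rests on far more extrapolation at the lower doses. At 100 h and LLOQ 1% the simulated SD of its slope was 0.11, against 0.06 for AUC0-192.

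Second, relevant text is not visible. Protocol section 2.2 is cited but not shown, the numbering skips 7.3.3, and SAP section 7.5.2 appears only as a heading. The SAP abbreviation list defines DB as "Dose Proportionality, Between-Subject Design", a term used nowhere in the visible text. The protocol also defines AUC0-24 and %AUCtz-∞. A reader might infer that no common-window analysis was planned. The documents do not support that, and no omission is claimed.

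Third, the size rests wholly on assumed inputs, and some cells in step 3 are pure LLOQ truncation. This stands. Sampling 200 mg to 672 h suggests that late levels were thought possible, but does not show it.

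Fourth, no hypothesis is tested, and dose escalation rests on safety data (protocol section 3.1). This also stands.

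**Conclusion.** The conditional statement holds: whenever 200 mg tz exceeds 192 h, the AUC0-tz slope of a proportional drug is biased upward. Under the stated model the bias runs from about 0.00 at a 24 h half-life to 0.35 at 150 h. It may be negligible, part or all of it may be LLOQ truncation, and it often lies within the confidence interval.

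Two stronger readings are tempting. One is that the plan will hide less-than-proportional exposure. Step 5 shows this is material only at long half-lives: a true 0.78 reads as 1.01 at 100 h but as 0.84 at 50 h and 0.79 at 24 h. The documents give no half-life that would place the drug there. The other is that the dose-proportionality assessment as a whole is invalid. The Cmax slope is untouched, and the AUC0-∞ slope is sound in principle.

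Severity is minor to moderate: an avoidable, directional artefact in one of three exploratory slopes.

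**What to change.** Unless protocol sections 2.2 and 7.3.3 or SAP section 7.5.2 already do this:

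- Keep all planned slopes and add a supportive power-model fit on AUC0-192, since 192 h is sampled in all three groups.
- State the rule for subjects with tz before 192 h. One option is to extrapolate from tz to 192 h with the subject's own terminal slope where estimable, otherwise treat the value as not evaluable, and report the extrapolated share.
- Show tz and %AUCtz-∞ by dose beside the slopes. If both are already listed parameters, this is only a matter of placement.
- Where 200 mg tz exceeds 192 h, report any difference between the AUC0-tz and AUC0-192 slopes, and do not read the AUC0-tz slope on its own as evidence on dose proportionality.

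The cost is one more non-compartmental parameter, one more model run on existing samples and a few sentences.

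There are downsides. AUC0-192 pulls true non-proportionality toward 1. For a true 1.29 it is further from the truth than AUC0-tz at 36 and 50 h, so it is a companion to AUC0-∞ and not a replacement. It is also partly extrapolated when tz is early: for 50 mg at LLOQ 5%, by 24, 13 and 5% at half-lives of 36, 50 and 75 h. AUC0-24 is no substitute, since at 50, 75 and 100 h it covers only 26, 18 and 14% of AUC0-∞, against 93, 83 and 73% for AUC0-192.

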### 7.3.4 Safety analyses

Safety will be assessed as defined by the endpoints listed in Section [2.1.2](#) and 2.2.2 based on the treated set (TS). Safety analyses will be descriptive in nature and will be based on BI standards.

For all analyses the treatment actually administered (= treatment at onset) to the subject will be used (any deviations from the randomised treatment will be discussed in the minutes of the Report Planning Meeting).

Treatments will be compared in a descriptive way. The placebo group in the safety evaluation will consist of all subjects treated with placebo, regardless of the dose group in which they were treated. The test treatment groups will be compared to the placebo group in a descriptive way. Tabulations of frequencies/proportions will be used for the evaluation of categorical (qualitative) data, and tabulations of descriptive statistics will be used to analyse continuous (quantitative) data.

Measurements (such as ECGs, vital signs, or laboratory parameters) or AEs will be assigned to treatments (see Section [5.2](#)) based on the actual treatment at the planned time of the measurement or on the recorded time of AE onset (concept of treatment-emergent AEs).

Therefore, measurements planned or AEs recorded prior to intake of trial medication will be assigned to the screening period, those between trial medication intake until the trial termination date will be assigned to the treatment period. These assignments including the corresponding time intervals will be defined in detail in the trial statistical analysis plan (TSAP). Note that AEs occurring after the last per protocol contact but entered before database lock will be reported to Pharmacovigilance only and will not be captured in the trial database.

Additionally, further treatment intervals (called analysing treatments) may be defined in the TSAP in order to provide summary statistics for other than above periods, such as combined treatments, on-treatment totals, or periods without treatment effects (such as screening and post-study intervals).

Adverse events will be coded using the Medical Dictionary for Regulatory Activities (MedDRA). Frequency, severity and causal relationship of AEs will be tabulated by

Proprietary confidential information © 2019 Boehringer Ingelheim International GmbH or one or more of its affiliated companies

treatment, system organ class and preferred term. SAEs, AESIs (see Section [5.2.6.1](#)) and other significant AEs (according to ICH E3) will be listed separately.

Previous and concomitant therapies will be presented per treatment group without consideration of time intervals and treatment periods. Laboratory data will be compared to their reference ranges. Values outside the reference range as well as possibly clinically significant values will be highlighted in the listings. Additionally, differences from baseline will be evaluated.

Vital signs or other safety-relevant data will be assessed with regard to possible on-treatment changes from baseline.

The ECG variables QT, HR, QTcF, QTcB, PR, QRS, and RR obtained from the centralised evaluation of 12-lead ECG recordings will be the basis for the derivation of quantitative and categorical ECG endpoints. These endpoints and their analyses will be described in the TSAP.

## **7.4 INTERIM ANALYSES**

No formal interim analysis is planned. If considered necessary, an exploratory PK analyses will be performed based on planned sampling times.

## **7.5 HANDLING OF MISSING DATA**

### **7.5.1 Safety**

It is not planned to impute missing values for safety parameters.

### **7.5.2 Pharmacokinetics**

Handling of missing PK data will be performed according to the relevant Corporate Procedure ([001-MCS-36-472](#)).

PK parameters that cannot be reasonably calculated based on the available drug concentration-time data will not be imputed.

## **7.6 RANDOMISATION**

Subjects will be randomised within each dose group in a 3:1 ratio (test treatment to placebo).

The sponsor will arrange for the randomisation as well as packaging and labelling of trial medication. The randomisation list will be generated using a validated system that uses a pseudo-random number generator and a supplied seed number so that the resulting allocation is both reproducible and non-predictable.

The randomisation list will contain additional blocks to allow for subject replacement (refer to Section [3.3.5](#)).

## **7.7 DETERMINATION OF SAMPLE SIZE**

It is planned to include a total of 24 subjects in this trial. The planned sample size is not based on a power calculation. The size of 8 subjects per dose group (6 on active treatment, and 2 on placebo) is commonly used in single-rising dose studies of the present type and is in general considered as sufficient for the exploratory evaluation of single dose safety and pharmacokinetics.

## **8. INFORMED CONSENT, TRIAL RECORDS, DATA PROTECTION, PUBLICATION POLICY, AND ADMINISTRATIVE STRUCTURE**

The trial will be carried out in compliance with the protocol, the ethical principles laid down in the Declaration of Helsinki, in accordance with the ICH GCP, relevant BI SOPs, the Japanese GCP regulations (Ministry of Health and Welfare Ordinance No. 28, March 27, 1997) and other relevant regulations. Investigators and site staff must adhere to these principles.

Standard medical care (prophylactic, diagnostic, and therapeutic procedures) remains the responsibility of the subject's treating physician.

The investigator will inform the sponsor immediately of any urgent safety measures taken to protect the trial subjects against any immediate hazard, as well as of any serious breaches of the protocol or of ICH GCP and the Japanese GCP regulations.

The Boehringer Ingelheim transparency and publication policy can be found on the following web page: [trials.boehringer-ingelheim.com](http://trials.boehringer-ingelheim.com). The rights of the investigator and of the sponsor with regard to publication of the results of this trial are described in the investigator contract. As a general rule, no trial results should be published prior to archiving of the CTR.

The terms and conditions of the insurance coverage are made available to the investigator and the subjects, and are stored in the ISF.

